## 1 LIST OF ABBREVIATIONS

AE	Adverse Event
BMI	Body Mass Index
BP	Blood Pressure
CRF	Case Report Form
CRO	Contract Research Organization
EDTA	Ethylene Diamine Tetra Acetic Acid
etc.	“and so forth”
e.g.	“for example”
et al	“and others”
g	Gram
g	gravity
GCP	Good Clinical Practice
Hb	Hemoglobin
HbA1c	Glycated hemoglobin
HR	Heart Rate
lbs.	Pounds
ICF	Informed Consent Form
ICH	International Conference of Harmonization
IRB	Institutional Review Board
kg	Kilogram
LOCF	Last Observation Carried Forward
MCH	Mean Corpuscular Hemoglobin
MCHC	Mean Corpuscular Hemoglobin Concentration
MCV	Mean Corpuscular Volume
QI	Qualified Investigator
RBC	Red Blood Cells
RDW	Red Cell Distribution Width
ROS	Reactive Oxygen Species
RNS	Reactive Nitrogen Species
SAE	Serious Adverse Event
SPH	Salmon Protein Hydrolysate
SST	Serum Separating Tube
WBC	White Blood Cell
WHO	World Health Organization

Protocol 18PEHH: A proof-of-concept study to evaluate the efficacy of Salmon Protein Hydrolysate Powder on energy increase and anti-inflammatory modulation in healthy males and females.

## 2 INTRODUCTION

In the United States, 38% of Americans report waking up and feeling tired for more than four days a week (Moore, 2015). During 2010-2011, 15.3% of women and 10.1% of men reported feelings of fatigue and exhaustion on most days or every day for 3 months (Blackwell, 2013). Increased lethargy and fatigue and decreased time and energy for nonwork-related activities may be contributed by a decreased amount of physiological energy to complete work-related tasks (Haas and Brownlie, 2001). This may ultimately lead to lower perceived overall quality of life.

Red blood cells are essential in oxygen transport thus making them an important part of health. Hemoglobin, the protein in red blood cells, is responsible for oxygen transport and plays an important role in oxygen transport and energy production. Iron is the essential element found in hemoglobin (Haas and Brownlie, 2001). Poor levels of red blood red cells, hemoglobin, and iron in the bloodstream has been implicated in sub-optimal oxygen transport and increased lethargy (Billett, 1990). In a placebo-controlled clinical trial, eight weeks of Salmon Protein Hydrolysate supplementation was shown to significantly increase red blood cells and hemoglobin enhance alertness, and energy in anemic individuals (Bomi et al., 2015).

Fatigue refers to a reduction of effort that may be caused by an imbalance in energy costs and expected reward of actions. It is one of the most common symptoms associated with immune system activation. Pro- and anti-inflammatory cytokines are released during an immune response. Cytokines induce behavioral alterations in the central nervous system through inducing modifications of neurotransmitters and brain functions. (Karshikoff et al., 2017). Salmon hydrolysate has been shown to augment cytotoxic activity of natural killer cells through enhancing T-helper cells and increasing the number of cytokines, implicating its immunomodulating effect (Kim, 2013).

The investigative product, Salmon Protein Hydrolysate (SPH), is produced by the solubilization of salmon flesh and enzymatic hydrolyzation of the protein. This process is done at very low temperatures to fully separate fat from protein and to prevent oxidation. SPH contains 620 bioactive peptides and 21 amino acids. The oil ingredient is readily absorbed without the action of pancreatic proteases due to its high concentration of short peptides and free amino acids (Nørgaard et al., 2012). The low molecular weight of short peptides also allows for greater solubility in water and fast uptake of nitrogen with over 98% digestibility.

The following open-label, proof-of-concept study will evaluate the effect of a 128-day salmon protein hydrolysate (ProGo®) supplementation on energy and anti-inflammatory modulation in healthy adults.

Protocol 18PEHH:	A proof-of-concept study to evaluate the efficacy of Salmon Protein Hydrolysate Powder on energy increase and anti-inflammatory modulation in healthy males and females.
------------------	--

### **3 STUDY OBJECTIVES**

The objective of this study is to evaluate the efficacy of Salmon Protein Hydrolysate Powder (ProGo®) on energy increase and anti-inflammatory modulation in healthy males and females

#### **Primary outcome:**

The change from baseline (Day 0) to end-of-study (Day 128) in energy level as assessed by a Vitality and Quality of Life Questionnaire after a 128-day supplementation with Salmon Protein Hydrolysate Powder (ProGo®)

#### **Secondary outcomes:**

1. Change from baseline to Day 128 in Red Blood Cell (RBC) count, RBC indices (MCV, MCH, MCHC), hematocrit, and Red Cell Distribution Width (RDW) after supplementation with Salmon Protein Hydrolysate Powder (ProGo®)
2. Change from baseline to Day 128 in Hemoglobin (Hb) after supplementation with Salmon Protein Hydrolysate Powder (ProGo®)
3. Change from baseline to Day 128 in relative expression of 84 stress genes (Section 14.5) as evaluated by oxidative stress-related gene RT Profiler PCR array after supplementation with Salmon Protein Hydrolysate Powder (ProGo®)
4. Change from baseline to Day 128 in total Reactive Oxygen Species/Reactive Nitrogen Species free radical activity assessed by ROS/RNS assay after supplementation with Salmon Protein Hydrolysate Powder (ProGo®)
5. Change from baseline to Day 128 in levels of human inflammatory cytokines (IL-1RA, IL-4, IL-6, IL-10, IL-11, IL-13 and TGF- $\beta$ ) as measured by the Multi-Analyte ELISArray after supplementation with Salmon Protein Hydrolysate Powder (ProGo®)
6. Change from baseline to Day 128 in glycated hemoglobin (HbA1c) and fasting glucose after supplementation with Salmon Protein Hydrolysate Powder (ProGo®)
7. Change in score of the Hair, Nails, and Skin Self-Assessment Questionnaire after 128-day supplementation with Salmon Protein Hydrolysate Powder (ProGo®)

[figure not shown]

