#### 4 STUDY DESIGN

This will be an open label study conducted at the KGK clinic in London, ON.

The planned sample size for this study is 20 participants (includes 20% attrition).

Study Arm	Number of Participants
Salmon Protein Hydrolysate (ProGo®)	N = 20

In order to evaluate primary, secondary, and safety outcomes, study assessments will be conducted at baseline and at Day 128.

Protocol 18PEHH:	A proof-of-concept study to evaluate the efficacy of Salmon Protein Hydrolysate Powder on energy increase and anti-inflammatory modulation in healthy males and females.
------------------	--

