### 7.1 Visit 1; Screening (Day -45 to Day -1) \*

*\* At the discretion of the Qualified Investigator, any participants falling outside of the screening window (Day -45 to Day -1) due to scheduling issues may be asked to repeat eligibility/screening procedures prior to enrolment.*

At screening, an informed consent form will be given to the potential volunteer. They will be required to read the information and will be given the opportunity to seek more information if needed, or provided with the option of taking the consent form home to review prior to making their decision. If agreeable, the volunteer will sign the consent form and receive a duplicate of the signed copy. Once consent has been obtained, the screening visit will proceed. Each volunteer will be sequentially assigned a screening number to be entered in the screening and enrollment log. No fasting is required for this visit.

Screening assessments include:

1. Obtain informed consent
2. Review inclusion and exclusion criteria
3. Review medical history and capture recurring conditions
4. Review concomitant therapies and current health status
5. Weight and height measurements for BMI calculation (Section 7.5.2)
6. Waist and hip circumference measurements (Sections 7.5.3 and 7.5.4)
7. Seated resting blood pressure and heart rate measurements (Section 7.5.5)
8. Urine pregnancy test for female participants of child bearing potential
9. Physical Examination (excludes genital and rectal examination)
10. Collect blood sample for CBC
11. Administer Product Tolerance Questionnaire to assess participants' response to product (see 14.2)

The next visit will be scheduled for potentially eligible participants in  $\leq 45$  days.

Reminders for participants prior to their next in-clinic visit:

1. Refrain from consumption of supplements as per Section 5.3.2.
2. Maintain current dietary and exercise habits
3. 8-hour fast prior to next visit

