### 7.2 Visit 2; Baseline (Day 0)

Eligible participants will return to the clinic for baseline assessments. An 8-hour fasting period is required for this visit.

Baseline (Day 0) assessments include:

1. Review inclusion and exclusion criteria
2. Review concomitant therapies and current health status and identify pre-emergent adverse events

Protocol 18PEHH: A proof-of-concept study to evaluate the efficacy of Salmon Protein Hydrolysate Powder on energy increase and anti-inflammatory modulation in healthy males and females.

3. Weight measurement (BMI calculation)
4. Waist and hip circumference measurements
5. Seated resting blood pressure and heart rate measurements
6. Urine pregnancy test for female participants of child bearing potential
7. Two buccal cell swabs will be collected for DNA analysis (Section 7.5.6)
8. Collect blood samples for future analysis (Section 7.5.8):
  - o Oxidative stress-related gene expression (Sections 7.5.8.1 and 14.5)
  - o Total ROS/RNS free radical activity (Section 7.5.8.2)
  - o Human inflammatory cytokine levels (Section 7.5.8.3)
9. Collect blood samples for HbA1c and fasting glucose
10. Complete Vitality and Quality of Life Questionnaire (Section 14.2)
11. Complete Hair, Nails, and Skin Self-Assessment Questionnaire (Section 14.4)
12. Dispense investigational product and instruct participants on use
13. Dispense study diary instructions for participants (record daily product use, changes in concomitant therapies, and any adverse events throughout the study).

The next visit will be scheduled for Week 18 (Day 128 ± 3).

Reminders for participants prior to their next in-clinic visit:

1. Follow instructions on consumption of the investigational product and log any irregularities or missed doses in the subject diary
2. Refrain from consumption of supplements as per Section 5.3.2.
3. Complete and bring subject diaries on the next visit if diary is not completed using the app
4. Maintain current dietary and exercise habits.
5. Bring unused investigational product in the original packaging to next visit.
6. 8-hour fast prior to next visit

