## 7.6 Laboratory Analyses

Blood samples will be drawn from the participants at screening (Visit 1), baseline (visit 2), and the end of Study (Visit 3) as indicated in the schedule of assessments. Blood draws will be performed from a participant's arm via venipuncture. See Section 11.3 for potential risks associated with venipuncture.

Protection of participant confidentiality will extend to all data generated from the assaying of these samples. These samples will be alphanumerically coded and the persons performing the analysis will not be aware of the subject's identity.

At screening (Visit 1), 4 mL of whole blood will be collected in:

1. 1 x 4 mL EDTA vacutainer tube to generate plasma for:
  - a. CBC (1 tube)

At baseline (Visit 2), 23 mL of 8 hour fasting whole blood will be collected in:

1. 1 x 4 mL EDTA vacutainer tube to generate plasma for:
  - a. HbA1c (1 tube)
2. 1 x 4 mL EDTA vacutainer tube for whole blood for:
  - a. Future analysis - Gene expression analysis (1 tube)
3. 3 x 5 mL SST vacutainer tube to generate serum for:
  - a. Future Analysis - ROS/RNS and Inflammatory Cytokines (2 tubes)
  - b. Fasting Glucose (1 tube)

At the end of the study (Visit 3), 27 mL of 8 hour fasting whole blood will be collected in:

1. 2 x 4 mL EDTA vacutainer tube to generate plasma for:
  - a. CBC (1 tube)
  - b. HbA1c (1 tube)
2. 1 x 4 mL EDTA vacutainer tube for whole blood for:
  - a. Future analysis - Gene expression analysis (1 tube)
3. 3 x 5 mL SST vacutainer tube to generate serum for:
  - a. Future Analysis - ROS/RNS and Inflammatory Cytokines (2 tubes)
  - b. Fasting Glucose (1 tube)

The total blood volume collection for the laboratory assessments listed above will be approximately 54 mL, over the period from screening to end of study (approximately 128 days). At any study visit, blood loss per volunteer is not expected to exceed 27 mL. Additional blood samples may be collected during the course of the study in order to perform or repeat laboratory tests outlined in the Schedule of Assessments if needed.

The central laboratory, Life Labs, London Ontario, will be used in this study to measure CBC, HbA1c, and fasting glucose.

Blood collected for future analysis will be shipped to the sponsor.

Urine pregnancy test will be performed at the KGK Science clinic site.

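### No CBC is scheduled at Day 0, so the red-cell and hemoglobin outcomes have no baseline as defined, and the plan does not name the screening CBC in its place

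*Combined protocol and SAP*

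**What the plan says.** Section 3 defines secondary outcome 2 as "Change from baseline to Day 128 in Hemoglobin (Hb") and gives outcome 1 (RBC count, red-cell indices, hematocrit, RDW) the same form. Baseline is tied to a day in the primary outcome: "The change from baseline (Day 0) to end-of-study (Day 128"). Visit 2 is the only visit headed as baseline. Section 4 says that, for primary, secondary and safety outcomes alike, "study assessments will be conducted at baseline and at Day 128".

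The procedures do not match this for the CBC:

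- Section 7.1 (screening, Day -45 to Day -1) includes "Collect blood sample for CBC" and states "No fasting is required for this visit".
- Section 7.2 (Day 0) opens with "Eligible participants will return to the clinic for baseline assessments. An 8-hour fasting period is required for this visit". Its blood samples are those for gene expression, ROS/RNS, cytokines, HbA1c and glucose. CBC is not among them.
- Section 7.6 says "At baseline (Visit 2), 23 mL of 8 hour fasting whole blood will be collected in" a set of tubes, none of which is for CBC.
- Section 7.4 (Day 128 ± 3, fasting) includes a CBC.
- The schedule in 14.1 marks CBC at Visits 1 and 3 only.

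Section 9.3 tests whether the mean change from baseline differs from zero. Section 9.3.2 summarizes changes from baseline for continuous safety variables. Neither says which CBC is the baseline.

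**The concern.** Outcomes 1 and 2 need a Day 0 value that the plan never collects. Whoever analyzes the data will have to substitute the screening CBC without any written instruction.

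This matters because the study has one arm and the test is of mean change against zero. If the start point is the screening sample, whatever happens before the first dose counts as change on product, and the length of that pre-dose period differs between participants. The documents give one reason why status could shift in it. Section 5.3.2 admits some supplement users after a two-week washout, and the reminder to abstain comes at the end of the screening visit, so some screening samples may precede the washout.

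Three smaller points follow:

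- Fasting is uncontrolled at screening but required at Day 128.
- Screening hemoglobin and hematocrit also decide the anemia exclusion (5.2, criterion 17). Using the same values as baseline invites some regression to the mean, here towards a fall.
- A participant who repeats screening has two pre-dose CBCs and no rule for choosing between them.

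Red cells and hemoglobin are not peripheral: Section 2 offers them as a mechanism for the energy effect.

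**Working it through.** **1. Is a Day 0 CBC hidden in the blood volumes?** Tube volumes from Section 7.6:

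| Visit | Tubes | Sum | Stated |
|---|---|---|---|
| 1 | CBC 4 | 4 mL | 4 mL |
| 2 | HbA1c 4 + gene expression 4 + SST 3 × 5 | 23 mL | 23 mL |
| 3 | CBC 4 + HbA1c 4 + gene expression 4 + SST 3 × 5 | 27 mL | 27 mL |
| Total | 4 + 23 + 27 | 54 mL | about 54 mL |

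Every stated volume is reproduced. Visits 2 and 3 differ by 27 − 23 = 4 mL, which is exactly the CBC tube. No CBC is drawn at Day 0.

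**2. Is the CBC an exception?** In 14.1 the questionnaires, HbA1c, glucose, gene expression, ROS/RNS, cytokines and vital signs all have a Visit 2 entry. The CBC is the only measured outcome without one.

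**3. How many variables?** Secondary: RBC, MCV, MCH, MCHC, hematocrit, RDW, Hb = 7. Safety outcome 2: WBC 1 + differential 5 + platelets 1 = 7. Total 14.

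**4. Interval between the two CBCs.** Inputs: screening Day -45 to Day -1 (7.1); Visit 3 at Day 128 ± 3, that is Day 125 to Day 131 (7.4).

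- Shortest: 125 − (−1) = 126 days.
- Longest: 131 − (−45) = 176 days.
- Spread: 176 − 126 = 50 days.
- For outcomes measured at Day 0: 125 to 131 days, a spread of 6 days.

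**5. Off-product share of the CBC interval.** Share = pre-dose days / (pre-dose days + days from Day 0 to Visit 3), taking dosing to start at Day 0.

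- Minimum: 1 / (1 + 131) = 1/132 = 0.8%.
- Maximum: 45 / (45 + 125) = 45/170 = 26.5%.

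These are the limits of the permitted windows. They are shares of elapsed time, not of the observed change.

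**6. Does any other provision fill the gap?**

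- LOCF (9.3) would at most carry the screening value to Day 0, if a test that was never scheduled counts as missing at all. It is barred for safety variables, so hemoglobin would receive a Day 0 value while WBC and platelets from the same tube would not.
- The allowance in 7.6 for additional samples is optional and schedules nothing at Day 0.

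**The case against.** The best reply is that no endpoint is lost. Outcomes 1 and 2 say baseline without adding a day, there is one scheduled pre-dose CBC, and the visit list, tube list and schedule agree with each other. The timing therefore looks deliberate, and one CBC serving both eligibility and baseline is a workable design. On that view a single defining sentence is enough. This stands in part: a paired change can be calculated, and the wording-only repair is legitimate. It does not remove the conflict, because Section 4 and the Visit 2 heading put baseline at Day 0 and nothing makes an exception for the CBC.

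Other objections also have force:

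- The percentages are window extremes. The documents give no distribution of screening gaps and no drift in red-cell measures, and participants are asked to keep diet and exercise stable. No size of bias is claimed.
- Screening samples are of uncontrolled fasting status, not known to be fed, and the documents give no fasting effect on a CBC. The mismatch is a secondary point.
- Section 7.1 also says the next visit falls within 45 days. However, its footnote says only that participants outside the window "may be asked to repeat eligibility/screening procedures prior to enrolment", so the limit is not firm.
- Safety outcome 2 is worded as an effect of supplementation and summarized descriptively, so the seven safety parameters carry less weight than the seven tested endpoints. Their change-from-baseline summaries still lack a defined start.
- A Day 0 CBC would not supply a control.

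**Conclusion.** The concern holds. Secondary outcomes 1 and 2 cannot be obtained as Sections 3 and 4 define them, because no CBC is taken at Day 0 and no section appoints the screening CBC instead. Seven tested secondary endpoints are affected, plus the change summaries for seven safety parameters. Under the stated windows the available change covers 126 to 176 days, of which 1 to 45 days precede dosing. Both upper figures would rise if a screening sample older than 45 days were accepted.

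This rests on reading baseline as Day 0 throughout and on dosing from Day 0. The direction and size of any resulting bias cannot be derived from the documents. The primary outcome and N = 20 are untouched. It should be fixed before enrolment, since a Day 0 sample that was not taken cannot be recovered.

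**What to change.** **Preferred.** Add a CBC with differential to Visit 2 in Sections 7.2, 7.6 and 14.1 (one 4 mL EDTA tube). Name it as the baseline for secondary outcomes 1 and 2 and safety outcome 2, and keep the screening CBC for eligibility. In 7.6, Visit 2 becomes 23 + 4 = 27 mL, equal to the per-visit maximum already expected there, and the total becomes 54 + 4 = 58 mL. This removes both the variable pre-dose interval and the fasting mismatch.

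**Fallback.** Redefine these outcomes in Sections 3, 4, 9.3 and 9.3.2 as change from screening to Day 128. State which CBC counts when screening is repeated, and report each participant's interval in days.

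**Cost.** The preferred option needs about 20 routine CBCs at a venipuncture that already takes place, with no extra visit. The fallback needs wording only. If the protocol has already been approved, either option requires a documented amendment under Sections 7.8 and 9.5, which may need IRB and Health Canada review.

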#### **Safety outcomes:**

1. The incidence of pre-emergent and post-emergent adverse events following a 128-day supplementation
2. The effect of a 128-day supplementation on complete blood count which includes: hematology (WBC) count with differential (neutrophils, lymphocytes, monocytes, eosinophils, basophils) and platelet count
3. The effect of a 128-day supplementation on vital signs: weight, blood pressure (BP) and heart rate (HR), and waist and hip circumference

Protocol 18PEHH:

A proof-of-concept study to evaluate the efficacy of Salmon Protein Hydrolysate Powder on energy increase and anti-inflammatory modulation in healthy males and females.

#### 4 STUDY DESIGN

This will be an open label study conducted at the KGK clinic in London, ON.

The planned sample size for this study is 20 participants (includes 20% attrition).

Study Arm	Number of Participants
Salmon Protein Hydrolysate (ProGo®)	N = 20

In order to evaluate primary, secondary, and safety outcomes, study assessments will be conducted at baseline and at Day 128.

Protocol 18PEHH:	A proof-of-concept study to evaluate the efficacy of Salmon Protein Hydrolysate Powder on energy increase and anti-inflammatory modulation in healthy males and females.
------------------	--

## 5 SELECTION OF STUDY POPULATION

This study will enroll 20 healthy males and females. Each participant must fulfill the inclusion criteria and not meet any of the exclusion criteria as described in sections 5.1 and 5.2, respectively.

### 5.1 Inclusion Criteria

1. Healthy male or female, 30-60 years of age
2. Female participant is not of child bearing potential, defined as females who have had a hysterectomy or oophorectomy, bilateral tubal ligation or are post-menopausal (natural or surgically with > 1 year since last menstruation)

or,

Females of childbearing potential must agree to use a medically approved method of birth control and have a negative urine pregnancy test result. All hormonal birth control must have been in use for a minimum of three months. Acceptable methods of birth control include:

- Hormonal contraceptives including oral contraceptives, hormone birth control patch (Ortho Evra), vaginal contraceptive ring (NuvaRing), injectable contraceptives (Depo-Provera, Lunelle), or hormone implant (Norplant System)
- Double-barrier method
- Intrauterine devices
- Non-heterosexual lifestyle or agrees to use contraception if planning on changing to heterosexual partner(s)
- Vasectomy of partner (shown successful as per appropriate follow-up)

3. BMI of 18.5 kg/m^2-32.5 kg/m^2
4. Agrees to comply with study procedures
5. Willing to commit to taking product for 128 days (See questionnaire in 14.2)
6. Agrees to provide voluntary, written, informed consent to participate in the study
7. Agrees to maintain normal diet and exercise routine throughout the study
8. Healthy as determined by medical history, medical physical test for good health, and laboratory results

